2.4.2 Prior, concomitant and post therapies

Prior medications are defined as drugs taken and stopped prior to the first administration of study treatment. Any medication given at least once between the day of the first dose of the study treatment and the end of study visit will be a concomitant medication. Prior or concomitant medication will be identified based on recorded or imputed start and end dates of taking the medication.

Prior and concomitant medication will be summarized by treatment group (separately for ocular and non-ocular medications/therapies), presented in alphabetical order by ATC classification codes and preferred term. The tables will be presented with overall number and percentage of subjects receiving at least one drug of a particular ATC code and at least one drug in a particular

Novartis	For business use only	Page 14 of 33
SAP		CSAF312B12201

preferred term. Medications will be coded according to the WHO Drug Reference List dictionary.

In addition, all information will be listed including the reported name, laterality, and treatment start/end date, etc.

2.4.3 Rescue medication

There is no rescue medication that will be proactively provided to study sites or subjects. However, at the discretion of the investigator, medication (local or systemic, over the counter or prescription) used for pain relief will be allowed and will be specified if used for ocular or non-ocular pain. Rescue medication will be the newly assigned medication for pain (ocular or non-ocular) during treatment period. Pain medication used as background therapy will not be counted as rescue medication.

The number and percentage of subjects who received any rescue medication will be summarized by treatment group. The 7-day frequency of rescue medication use will be summarized by week and treatment group.

2.4.4 Prohibited medication

Moreover, concomitant medications that are prohibited as per protocol (Table 2-2) and given during the conduct of the study will be provided. The number and percentage of subjects taking concomitant medications will be summarized by treatment group.

Table 2-2Prohibited medication

Medication	Prohibition period	Action taken
Artificial tears/gels/lubricant eye drops other than those started before enrollment	Study duration	No action
Use of topical ocular medications (prescription or over the counter) within 4 hours prior to a study visit	Study duration	Reschedule study visit outside of the 4 hour window
Use of ocular or oral pain medication within 4 hours of a study visit	Study duration	Reschedule the study visit outside of the 4 hour window
Ocular, nasal, inhaled, or systemic corticosteroids	Study duration	No action
Use of oral or topical ocular antihistamines, mast cell stabilizers (e.g. Ketotifen)	Study duration	No action
Neuromodulators and NGF for any reason	Study duration	Discontinue study treatment

Novartis	For business use only	Page 15 of 33
SAP		CSAF312B12201

2.5 Analysis of the primary objective

The primary objective of the study is to demonstrate the efficacy of at least 1 of 2 concentrations of SAF312 (5 mg/ml or 15 mg/ml) with superiority to placebo in reducing ocular pain severity.

For the purpose of the statistical analyses presented in this document, the following terminology is used:

- Intercurrent events (IE) Events that occur after treatment initiation and either preclude observation of the variable or affect its interpretation (e.g. rescue medications, discontinuation of treatment, switching treatment, terminal events such as death, etc.)
- Missing at Random (MAR) the multiple imputation model will be built based on similar patients (i.e. with the same covariates and observed measurement history) in the same treatment arm.
- Jump to Reference (J2R) the multiple imputation model will be built based on the available placebo data (including partial information from patients that discontinued prematurely). The imputation model will include important background characteristics and observed data.

2.5.1 Primary endpoint

The primary clinical question of interest is: What is the effect of SAF312 versus placebo on change from baseline in pain severity after treatment in subjects with CICP, had they not taken rescue or prohibited medications, and had they not discontinued treatment?

The justification for the primary estimands is that they will capture the effect of the study drug for the full duration when administered without confounding effects from prohibited medications or rescue medications. They also account for discontinuation from treatment due to AEs, lack of efficacy, and use of prohibited medications. The hypothetical strategy assumes the subjects with Intercurrent events (IEs) will behave like other subjects who did not take rescue/prohibited medications and stayed on study treatment.

The analysis of the primary endpoints will be based on FAS.

The primary estimand is defined as follows for signs and symptoms:

- The target **population** is subjects with CICP persisting at least 4 months after refractive surgery or cataract surgery, and chronicity of pain confirmed during the 3-month observation period who meet the inclusion and exclusion criteria.
- The primary **endpoint** is the change from baseline in ocular pain severity VAS at Week 12. The score is derived by averaging the seven daily measurements of each week.
- The treatment of interest is SAF312 arms versus placebo, had they not needed rescue or prohibited medications and behaved like other patients who did not take them, had they not discontinued treatment and behaved like other patients who did not discontinue treatment.

Table 2-3 The handling of intercurrent events strategy for primary estimands

Intercurrent Events	Strategy	

Novartis SAP	Fo	r business use on	ly Page 16 of 33 CSAF312B12201
Rescue reason	medications for pain relief due t	o any •	The data on the days will be excluded and treated as missing. Missing weekly mean pain score values will be handled under MAR assumption in MMRM
Prohibit primary •	ed medications that could confo endpoint (See Table 2-2) Ocular, nasal, inhaled, or syster corticosteroids Use of oral or topical ocular antihistamines, mast cell stabiliz	und the • mic zers	The data on the day(s) + 3 days following the last day of these prohibited medications will be excluded and treated as missing. Missing weekly mean pain score values will be handled under MAR assumption in MMRM
•	Any new use or change in dosir neuromodulators for any reasor use of topical ocular NGF	ng of • n, or any •	The data starting from the day will be excluded and treated as missing Missing weekly mean pain score values will be handled based on the MAR assumption in MMRM
Discont reasons	inuation of study treatment due t s (e.g. AEs, pandemic)	o any •	The data after study treatment discontinuation will be treated as missing. Weekly mean pain score values at or after the week of study treatment discontinuation will be handled under MAR assumption in MMRM

- The **summary measure** is the treatment difference of the variable means between SAF312 arms and placebo respectively.
 - o SAF312 15 mg/ml vs SAF312 placebo
 - o SAF312 5 mg/ml vs SAF312 placebo

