6.2.2 Prohibited medication

Use of the treatments displayed in the below table are not allowed starting from Screening Visit (Visit 1).

Table 6-2 Prohibited medication

Medication	Prohibition period	Action taken	
Use of topical ocular medications (prescription or over the counter) within 4 hours prior to a study visit	Study duration	Reschedule study visit outside of the 4 hour window	
Use of ocular or oral pain medication within 4 hours of a study visit	Study duration	Reschedule the study visit outside of the 4 hour window	
Ocular, nasal, inhaled, or systemic corticosteroids	Study duration	No action	
Use of oral or topical ocular antihistamines, mast cell stabilizers (e.g. Ketotifen)	Study duration	No action	
New use or change in dosing of neuromodulators for any reason, and any use of topical ocular NGF	Study duration	Discontinue study treatment	

All medications administered after the subject enrolls in the study must be listed on the Concomitant medications/Significant non-drug eCRF page.

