8.5 Additional assessments

8.5.1 Other Assessments

In vivo confocal microscopy is included as an exploratory assessment at select sites to evaluate corneal nerve morphology in patients with CICP.

The following ocular surface assessments (corneal and conjunctival staining, conjunctival redness, Schirmer's test) are included to evaluate whether long term inhibition of TRPV1 receptors with SAF312 eye drops has an adverse effect on ocular surface parameters.

Finally, the Pain Characterization questionnaire will be used to gain greater detail regarding the subject's ocular pain.

Frequency of artificial tear/gel/lubricant use and rescue medication use will be captured in the eDiary on a daily basis to gain insights to subject behavior with these products.

[figure not shown]

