12.4.6 Supplementary analysis

A supplementary clinical question of interest is: What is the effect of SAF312 versus placebo on change from baseline in weekly mean pain severity VAS score, regardless of discontinuation from study treatment discontinuations for any reason, and regardless of occasional use of rescue medication or prohibited medications?

The supplementary analysis to the primary analysis will be performed on the FAS population. The supplementary analysis will be performed using all observed data regardless of intercurrent events (a treatment policy strategy). The target population, the primary variable and the summary measure of the supplementary estimand for the supplementary estimand are the same as for the primary estimand. Differently from the primary estimand, this analysis considers all intercurrent events are inherent in the treatment regimen and will not exclude any observed data even when subjects take rescue/prohibited medications or discontinue treatment.

For subjects who use rescue medications for pain relief due to any reason, all observed data will be used for analysis. If not available, missing data will be under the MAR assumption for both SAF312 and placebo arms.

For subjects who take the following prohibited medications:

- Ocular, nasal, inhaled, or systemic corticosteroids
- Use of oral or topical ocular antihistamines, mast cell stabilizers

All observed data will be used for analysis. If not available, missing data on the day(s) +3 days of the IEs will be under the MAR assumption for both SAF312 arms and placebo arm.

For subjects with new use or change in dosing of neuromodulators for any reason or topical ocular NGF, all observed data will be used for analysis. If not available, missing data on the days of IEs will be under the MAR assumption for both SAF312 and placebo arms.

For subjects who discontinue from study treatment due to any reason, retrieved drop-out (RDO) data collected after study treatment discontinuation will be used for analysis. If not available, missing data after treatment discontinuation will be multiply imputed based on Jump to Reference assumption for SAF312 arms and under the MAR assumption for placebo arm.

The supplementary analysis will be performed using MMRM but includes all the observed data and imputed data if appropriate.

Subgroup analysis

Subgroup analyses of the primary endpoints will be outlined in the statistical analysis plan (SAP).

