5.1.2 Concomitant medication date imputation

5.1.2.1 Concomitant treatment end date imputation

- 1. If CM end day is missing and CM month/year are non-missing, then impute CM day as the minimum of treatment follow-up period date, date of death and the last day of the month.
- 2. If CM end month are missing and CM year is non-missing, then impute CM day as the minimum of treatment follow- up period date, date of death and the end of the year (31DECYYYY).
- 3. If CM end year value is missing, the date uncertainty is too high to impute a reliable date. Therefore, if the CM end year value is missing or ongoing, the imputed CM end date is set to NULL.
- 4. If imputed CM end date is less than the CM start date, use the CM start date as the imputed CM end date.

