5.1.2.2 Concomitant treatment start date imputation

The following table explains the notation used in the logic matrix. Please note that **missing start dates** will not be imputed.

	Day	Month	Year
Partial CMD Start Date	Not used	MON	YYYY
Treatment Start Date	Not used	TRTM	TRTY

The following matrix explains the logic behind the imputation.

	MON MISSING	MON < TRTM	MON = TRTM	MON > TRTM
YYYY	(1)	(1)	(1)	(1)
MISSING	Uncertain	Uncertain	Uncertain	Uncertain
YYYY < TRTY	(2.a)	(2.b)	(2.b)	(2.b)
	Before Treatment Start	Before Treatment Start	Before Treatment Start	Before Treatment Start
YYYY = TRTY	(4.a)	(4.b)	(4.a)	(4.c)
	Uncertain	Before Treatment Start	Uncertain	After Treatment Start
YYYY > TRTY	(3.a)	(3.b)	(3.b)	(3.b)
	After Treatment Start	After Treatment Start	After Treatment Start	After Treatment Start

1. If the CM start date year value is missing, the imputed CM start date is set to one day prior to treatment start date.

Novartis	For business use only	Page 26 of 33
SAP		CSAF312B12201

- 2. If the CM start date year value is less than the treatment start date year value, the CM started before treatment. Therefore:
 - a. If the CM month is missing, the imputed CM start date is set to the mid-year point (01JulYYYY).
 - b. Else if the CM month is not missing, the imputed CM start date is set to the midmonth point (15MONYYYY).
- 3. If the CM start date year value is greater than the treatment start date year value, the CM started after treatment. Therefore:
 - a. If the CM month is missing, the imputed CM start date is set to the year start point (01JanYYYY).
 - b. Else if the CM month is not missing, the imputed CM start date is set to the month start point (01MONYYYY).
- 4. If the CM start date year value is equal to the treatment start date year value:
 - a. And the CM month is missing, or the CM month is equal to the treatment start date month, then the imputed CM start date is set to one day prior treatment start date.
 - b. Else if the CM month is less than the treatment start date month, the imputed CM start date is set to the mid-month point (15MONYYY).
 - c. Else if the CM month is greater than the treatment start date month, the imputed CM start date is set to the month start point (01MONYYY).

If complete (imputed) CM end date is available and the imputed CM start date is greater than the (imputed) CM end date, then imputed CM start date should be set to the (imputed) CM end date.

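### Does the 3-day deletion tail after steroid, antihistamine or mast cell stabiliser use need a fuller definition in the primary analysis?

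*SAP*

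**What the plan says.** The primary estimand is hypothetical for prohibited medication (Protocol 2.1): the effect had subjects not taken it. SAP Table 2-3 and Protocol 12.4.3 implement this by deleting diary scores. For corticosteroids, oral or topical ocular antihistamines and mast cell stabilisers the rule is: "The data on the day(s) + 3 days following the last day of these prohibited medications will be excluded and treated as missing". Neither text defines a course or a gap that separates courses.

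Protocol 12.4.6 uses a similar window in the supplementary analysis, only for scores that were never observed: "missing data on the day(s) +3 days of the IEs will be under the MAR assumption".

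The two data sources differ in detail. Of the diary, Protocol 8.5.1 says: "Frequency of artificial tear/gel/lubricant use and rescue medication use will be captured in the eDiary on a daily basis". Other drugs go elsewhere. Under Protocol 6.2.2, "All medications administered after the subject enrolls in the study must be listed on the Concomitant medications/Significant non-drug eCRF page", and SAP 2.4.2 adds that "all information will be listed including the reported name, laterality, and treatment start/end date".

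On partial dates, SAP 2.4.2 says: "Prior or concomitant medication will be identified based on recorded or imputed start and end dates of taking the medication". If the day of the end date is missing, SAP 5.1.2.1 says to "impute CM day as the minimum of treatment follow-up period date, date of death and the last day of the month". For a partial start date in the treatment-start year, SAP 5.1.2.2 says that if "the CM month is greater than the treatment start date month, the imputed CM start date is set to the month start point".

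Weekly means use 7-day blocks from Day 1 (SAP 2.1.1.5), and one remaining score is enough (SAP 2.5.3.1). Table 6-2 attaches no action to use of these classes, so such subjects stay on treatment and keep filling in the diary.

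**The concern.** The phrase about the last day can be read in three ways for intermittent use:

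- **Per use:** delete each use day and the 3 days after it.
- **Single tail:** delete the use days, and 3 further days only after the last use in the study.
- **Per record:** delete from the start date of a medication record to its stop date plus 3 days.

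Two programmers could therefore build different primary datasets from the same subjects. For some use patterns the reading decides whether a Week 12 value exists, and Week 12 carries the primary inference. The text is also silent on whether imputed medication dates trigger deletion. If they did, a single day of use with an unknown day of the month could blank out several weeks. Such choices are best settled before anyone sees results by arm.

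**Working it through.** **The plan's own figure.** Inputs from SAP Section 3: difference 15 mm, SD 23 mm, 50 per arm, two-sided 5% adjusted for 2 comparisons, stated power about 83%. With alpha 0.05/2 = 0.025 and 98 degrees of freedom, the noncentrality is 15 / (23 × √(2/50)) = 15/4.6 = 3.26, and power is 83.6%. The stated figure reproduces.

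**Weekly means kept.** Inputs: 84 days (Protocol 6.1.4), 12 blocks of 7 days, one score sufficient. I deleted days under each reading and counted blocks with at least one day left. In the regular patterns use is already under way before Day 1 and lasts through Week 12.

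| Pattern of use | Per use | Single tail | Per record |
|---|---|---|---|
| Daily | 0 | 0 | 0 |
| Every 2, 3 or 4 days | 0 | 12 | 0 if entered as one record |
| Weekly | 12 | 12 | 0–1 if entered as one record |
| Two 5-day courses, Days 8–12 and 64–68 | 10 | 11 | 10 as two records |

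The second row follows directly. A use day plus 3 days covers 4 consecutive days, so use at gaps of 4 days or less leaves no day uncovered. With a single tail, 3 to 5 days of Week 12 remain. If first use falls on Day 2, 3 or 4, the 0 becomes 1.

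For the two courses, per-use deletion removes Days 8–15 and 64–71. That empties Week 2 (Days 8–14) and Week 10 (Days 64–70), so 12 − 2 = 10 remain. A single tail leaves Days 13 and 14 in place and saves Week 2, giving 11. Two dated records give the same 10 as per use. Only by merging courses 51 days apart into one record does the count fall to 3.

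**As-needed use** (simulation, 20,000 subjects):

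- On 20% of days, the mean number of weekly means kept is 10.0 per use, 12.0 with a single tail, and 1.5 if all use is one record. Week 12 is blank in 17%, 0.1% and 59%.
- On 30% of days, the means are 7.8, 12.0 and 1.0, with Week 12 blank in 37%, 0.5% and 76%.

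A blank Week 12 does not remove a subject from the repeated-measures model. Any earlier weeks still contribute under missing at random.

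**Trial level.** Suppose a fraction f of subjects dose every 2–4 days and lose every weekly mean. The effective size per arm is 50 × (1 − f). For f = 2%, 5% and 10% (assumed; the documents give no prevalence), n is 49, 47.5 and 45, and power is 82.7%, 81.4% and 79.0%. With a single tail it stays at about 83.6%.

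**Imputed dates.** I took one true use day with the day missing from both start and end, and averaged over all 84 study days and all 365 first-dose dates. Applying SAP 5.1.2 plus 3 days would delete 29 diary days and 3.5 weekly means on average. The exact date would delete about 4 days and no weekly mean. But SAP 2.4.2 uses imputed dates to classify a drug as prior or concomitant. Nothing there carries them over to diary deletion.

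**The case for a change.** The strongest case for a change is that the gap is real and closing it is cheap. The text names a last day but not of what. Because use of these classes carries no action, and the deviation table (SAP 5.3, COMD01) keeps such subjects in all analysis sets, this rule alone decides what they contribute. One sentence would settle it before unblinding.

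The ambiguity stands, and so does the 0-versus-12 arithmetic for its narrow pattern. The rest is weaker:

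- The 12-of-12 side needs day-level use dates and must ignore the stop date of every record but the last. The per-use and per-record readings are close to one rule applied to records of different detail, and for use every 2–4 days they agree.
- The wording in Protocol 12.4.6 leans towards a tail per event, but it covers only unobserved scores in the supplementary analysis. It does not govern the primary rule.
- The pattern should be uncommon. The classes are barred from Visit 1, 12 weeks before randomization. Exclusion 4 removes active seasonal allergic conjunctivitis, an obvious reason for these drugs, and exclusion 9 removes recent ocular or nasal steroid use.
- Protocol 11.2 already provides for queries on missing values, which covers partial dates.
- The treatment-policy supplementary analysis (Protocol 12.4.6, SAP 2.5.4.1) keeps scores recorded during prohibited-medication use, so a result without this deletion will be available.

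A related question is whether stable users of these classes may enter at all. Protocol 2.1 and 6.1.2 let treatment for underlying ocular conditions continue, Section 3 makes that conditional on eligibility, and Table 6-2 bars the classes. Reconciling those passages is for the sponsor. It does not bear on how the 3 days are counted.

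**Conclusion.** The concern does not call for a change. The rule leaves a small gap in definition, and the dated medication record gives a natural way to fill it: the last day is the stop date of each recorded course. The deletion serves the stated estimand, it is worded identically for all arms, and no reading is shown to favour either side. Protocol 6.4 keeps the trial team blind until database lock, so a programming choice made before then cannot follow the results.

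The loss is at most about 2 points of power if 5% of subjects dosed every 2–4 days (83.6% − 81.4% = 2.2) and under 5 points at 10% (83.6% − 79.0% = 4.6). These figures rest on assumed prevalences, on use from before Day 1 through Week 12, and on affected subjects losing every weekly mean. They also use a two-sample t calculation in place of the repeated-measures model. If the trial had many as-needed users each entered as one long record, the loss would be larger, but nothing in the documents points to that.

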2.5.2 Statistical hypothesis, model, and method of analysis

The primary objective of the study is to show that at least one SAF312 arm will improve weekly mean pain severity VAS score in comparison with its placebo by rejecting the null hypothesis below at a significance level α =0.05 (2-sided).

$$H_1: \mu_T = \mu_V \text{ vs. } H_2: \mu_T \neq \mu_V$$

where μ_T and μ_V are mean change from baseline of weekly mean pain severity VAS score in SAF312 arm and the placebo arm.

Dunnett procedure will be used to adjust overall type I error (0.05) among the comparisons between each SAF312 arm and the placebo arm.

Mixed model repeated measure (MMRM) analysis will be used with change from baseline at each week on treatment as response variable, and treatment, week and baseline score as covariates. Two interaction term (treatment*week and baseline*week) will also be included in the model.

Novartis	For business use only	Page 17 of 33
SAP		CSAF312B12201

An unstructured within subject correlation structure will be used for covariance matrix. If the unstructured covariance matrix results in a lack of convergence, then other covariance structures will be investigated. Toeplitz, First Order Autoregressive AR(1) and Compound Symmetry will be applied, in the specified order, until the model converges.

The Kenward-Roger approximation will be used to estimate denominator degree of freedom. REML (residual/restricted maximum likelihood) method will be used to estimate parameters.

The two-sided p value for the least square mean (LSM) difference between the SAF312 and the placebo group at each week will be reported for the difference. The primary inference will be based on LSM difference at Week 12 (Visit 6).

Line plots (LSM \pm 1 SE) will be presented by treatment groups and post-baseline day/visit. The x-axis will be study visit and the y-axis will be the change from baseline value.

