Potential participants will be required to provide written informed consent prior to any studyspecific Screening procedures being performed. Once informed consent is obtained subjects will be evaluated for eligibility based on the inclusion and exclusion criteria. Final eligibility will be based on an assessment of the subject's pain severity VAS prior to randomization, as well as their response to a single drop of topical ocular anesthetic (e.g. tetracaine, proparacaine eye drops per clinical practice). Response to anesthetic is defined as $a \ge 60\%$ reduction in ocular pain within 5 minutes after instillation of the anesthetic drop. The use of the anesthetic test is necessary for the selection of subjects with a primarily peripheral neuropathic type pain (i.e. primarily resulting from stimulation of the peripheral neuropathic pain are unlikely to experience significant improvement with a topical ocular treatment targeting the peripheral nerves.

Overall, approximately 150 subjects will be enrolled in the study. Subjects who meet eligibility criteria at Visit 2 will be randomized to one of the 3 treatment groups (SAF312 5 mg/mL, SAF312 15 mg/mL, or placebo) in a 1:1:1 ratio. Randomization will be stratified according to baseline mean pain severity over the 7 days prior to Baseline Visit (\geq 75 mm or <75mm).

No interim analysis planned.

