2.5.4 Supportive analyses

The subgroup analyses will be conducted to assess the consistency of treatment effect across various subgroups described in Section 2.2.1. Subgroup analyses will be conducted using the same model and analysis strategies described in the primary analyses but fitted by category of each of the subgroups. Subgroup variables that are used as fixed effects in the model will be removed from the model statement in the subgroup analysis if applicable. Subgroups will be presented graphically using forest plots. If a subgroup has limited number of subjects, the analyses on this subgroup may fail to converge and not be implemented. Instead, summary statistics for subgroup will be provided.

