2.5.4.1 Supplementary estimand

The target population, the primary variable and the summary measure of this estimand are the same as for the primary estimand. The supplementary estimand is defined to estimate the treatment effect of SAF312 versus placebo, regardless of occasional rescue medication, prohibited medications and treatment discontinuations due to any reason.

Novartis	For business use only	Page 18 of 33
SAP		CSAF312B12201

The justification for the supplementary estimand is that they will capture the effect of the study drug when administered in the real world with intercurrent events considered as inherent in the treatment regimen.

Table 2-4	The handling of intercurrent events strategy for supplementary
	estimands

Intercurrent Events	Strategy
Rescue medications for pain relief due to any reason	 All observed data will be used for analysis
	 Missing weekly mean pain score values will be multiple imputed under MAR assumption
Prohibited medications that could confound the primary endpoint (See Table 2-2)	 All observed data will be used for analysis
 Ocular, nasal, inhaled, or systemic corticosteroids 	 Missing weekly mean pain score values will be multiple imputed under MAR
Use of oral or topical ocular antihistamines, mast cell stabilizers	assumption
 Any new use or change in dosing of neuromodulators for any reason, or any 	 All observed data will be used for analysis
use of topical ocular NGF	 Missing weekly mean pain score values will be multiple imputed under MAR assumption
Discontinuation of study treatment due to any reason	 Weekly mean pain score values at or after the week of study treatment discontinuation will be multiple imputed based on J2R assumption for the SAF312 arms and under MAR assumption for the placebo arm

Mixed model covariance matrix will be handled in the same manner as primary estimand.

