2.14 Interim analysis

Not applicable.

3 Sample size calculation

Assuming a true treatment difference in change from baseline in weekly mean pain severity VAS of 15 mm and a SD of 23 mm, a sample size of 50 subjects per arm provides approximately 83% power that the primary analysis will be statistically significant at the two-sided 5% significance level adjusted by 2 comparisons.

See Table 3-1 for power to detect a significant difference from placebo under various assumed treatment-effect of weekly mean pain severity VAS and SD.

Query Advisor 7.0 is used for the estimate.

Novartis	For business use only	Page 23 of 33
SAP		CSAF312B12201

Table 3-1Power to detect a significant difference from placebo under different
assumed treatment effects and SD with N = 50 pts/arm

	Treatment effect: difference from placebo in change from baseline in weekly mean pain severity VAS	
SD of change from baseline in weekly mean I pain severity VAS	15	20
17	98%	>99%
20	92%	>99%
23	83%	97%

The sample size may increase by up to 20% (i.e. 60 pts/arm) in order to maintain power in case dropout increases during the pandemic.

4 Change to protocol specified analyses

Not applicable.

5 Appendix

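### If the unstructured covariance does not converge, every named fallback assumes equal variance at all 12 weeks, so the Week 12 standard error would be wrong if the variance differs between weeks

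*SAP*

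**What the plan says.** SAP 2.5.2 models change from baseline at each on-treatment week, with treatment, week, baseline, treatment-by-week and baseline-by-week terms, fitted by REML with Kenward-Roger degrees of freedom. The covariance is unstructured. If that fails to converge, "Toeplitz, First Order Autoregressive AR(1) and Compound Symmetry will be applied, in the specified order, until the model converges". No heterogeneous-variance form and no robust standard error is named. The same section bases primary inference on the Week 12 difference in least-squares means and states that "Dunnett procedure will be used to adjust overall type I error (0.05) among the comparisons".

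Protocol 12.4.2 names only the unstructured covariance and has no fallback. The rule is carried beyond the primary analysis. For the supplementary estimand (SAP 2.5.4.1), "Mixed model covariance matrix will be handled in the same manner as primary estimand". Subgroup analyses (SAP 2.5.4) are run "using the same model and analysis strategies described in the primary analyses but fitted by category of each of the subgroups".

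**The concern.** Toeplitz, AR(1) and compound symmetry, as named, differ only in how they model correlation. All three estimate a single variance for every week. Under any of them the Week 12 standard error comes from a variance pooled over Weeks 1 to 12. If the true Week 12 variance is above the pooled value, the standard error is too small and the trial exceeds its 5% family-wise level. If it is below, the standard error is too large and power is lost. Kenward-Roger makes small-sample corrections within the assumed covariance model and cannot detect that the model is wrong.

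The design gives some reason to expect a rise. Baseline is the mean of the 7 days before first dose (Protocol 12.4.1) and Week 1 starts on study day 1 (SAP 2.1.1.5). After adjustment for baseline by week, the residual variance is roughly σ²(1 − ρ²), where ρ is the correlation of that week with baseline. Week 1 adjoins the baseline week, so ρ should be highest there and fall later. This is reasoning, not a figure from the documents.

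**Working it through.** **Inputs from the documents.** Two active arms against placebo, 1:1:1, 50 per arm (SAP 1.1 and 3); SD 23 mm and difference 15 mm (SAP 3); two-sided 5% with Dunnett (SAP 2.5.2); 12 weekly means.

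**Assumed, because the documents are silent.** The SD at each week, the between-week correlation, and complete data.

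**1. The plan's own figure.** SAP 3 states that "a sample size of 50 subjects per arm provides approximately 83% power". The standard error is 23 × √(2/50) = 4.60 mm, and 15/4.60 = 3.26. A two-sample t-test (98 df) at 0.05/2 gives 83.6% power. With the Dunnett critical value it is 84.7% per comparison. The stated figure reproduces.

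**2. Parameters.** Unstructured: 12 × 13/2 = 78. A heterogeneous fallback has 12 variances where the homogeneous one has 1, so 11 more.

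**3. Standard error ratio.** With complete data and every covariate crossed with week, the Week 12 estimate is the same under any covariance structure; only its standard error changes. Under compound symmetry the ratio of the reported to the correct standard error is

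r = √(mean of the 12 weekly variances) / (Week 12 SD).

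For an SD rising linearly from 17 to 23, the mean SD is 20 and the step is 6/11 = 0.545. The mean variance is 20² + 0.545² × 143/12 = 403.5, so r = 20.09/23 = 0.873. The reported standard error is then 20.09 × 0.2 = 4.02 mm instead of 4.60 mm. For Toeplitz and AR(1), r was found by fitting each structure to the assumed covariance in large samples.

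**4. Family-wise error.** This is P(max|Z| > 2.212 × r) for two contrasts with correlation 0.5, where 2.212 is the large-sample Dunnett critical value. Only the shape of the SD path matters, not its absolute level.

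| Assumed SD, Week 1 to Week 12 (mm) | r | Family-wise error |
|---|---|---|
| 23 throughout | 1.00 | 5.0% |
| 20 to 23, linear | 0.94 | 7.0-7.1% |
| 18 to 23, linear | 0.89-0.90 | 8.6-8.7% |
| 17 to 23, linear | 0.87-0.88 | 9.5-9.7% |
| 16 to 23, linear | 0.85-0.86 | 10.4-10.7% |
| 14 to 23, linear | 0.81-0.82 | 12.3-12.8% |
| 10 to 23, linear | 0.74-0.76 | 16-18% |
| 17 to 23, plateau at Week 4 | 0.96 (CS) | 5.9% CS, 6.6% AR(1) |
| 12 to 23, plateau at Week 4 | 0.93 (CS) | 7.4% CS, 8.8% AR(1) |
| 28 to 23, falling | 1.11 | 2.6% |
| 23 to 17, falling | 1.18 (CS) | 2.0% |

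Ranges cover the three structures and several true correlation patterns (AR(1) with 0.9, compound symmetry with 0.7, a mixture of the two types and, for most rows, AR(1) with 0.95). The plateau rows and the last row are simulated under AR(1) and compound symmetry. The large-sample fit puts Toeplitz in the same 6-9% band for the plateau paths. On the linear paths the three structures agree closely, so the order of the cascade gives no protection.

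**5. Simulation check.** With 3 × 50 subjects and 6,000 runs per path, the Monte Carlo standard error at 5% is √(0.05 × 0.95/6000) = 0.28 points. AR(1) and compound symmetry gave 7.1% for the rise from 20 and 10.1-10.2% for the rise from 17. The unstructured model gave 4.7-5.3% on every path.

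**6. Does the remedy work?** In large-sample fits to the linear rises from 20, 17 and 14, heterogeneous Toeplitz and ARH(1) gave r = 1.000 and 5.0%. Heterogeneous compound symmetry gave 3.4-5.0%: conservative if the correlation decays with time, and not inflated in any case tried. These three were not simulated at 50 per arm.

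**The case against.** The risk needs two things to happen: the unstructured fit fails, and the variance differs between weeks. Neither is established. With complete data each week has four mean parameters (three arms and baseline), leaving 150 − 4 = 146 degrees of freedom for a 12 × 12 matrix, so 78 parameters are not in themselves a difficulty. Failure would have to come from missing weeks, and SAP 2.5.3.1 keeps a weekly mean even when only one daily value exists. On the other side, SAP 2.5.1 sets data to missing after rescue, prohibited medication and discontinuation, and SAP 2.5.2 itself provides for non-convergence. The branch is possible, with no stated probability.

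The direction of the error is also open. The documents give a single SD per scenario, and a falling SD makes the fallback conservative. That stands, and it is why the whole range is shown.

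A reader might infer that the problem is worst in the supplementary and subgroup analyses, because the same covariance rule serves them. The documents do not support this. Table 2-4 of the SAP multiply imputes missing weekly means for the supplementary estimand, so those datasets should be close to complete, where the unstructured model is easiest to fit. SAP 2.5.4 already replaces a small subgroup's model by summary statistics if it does not converge, and no family-wise claim attaches to subgroups.

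Finally, the arithmetic assumes complete data. With dropout the Week 12 estimate, and not only its standard error, would depend on the structure chosen. The figures do not cover that.

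**Conclusion.** The point holds as a conditional weakness. If the unstructured model fails, all three pre-specified fallbacks impose equal variance over time, and nothing in the plan protects the Week 12 standard error if that is untrue. Under the paths tried, family-wise error runs from about 2% (falling SD), through 5% (equal SDs) and about 6-9% (plateau at Week 4), to about 7-13% for a steady rise to 23 mm from a Week 1 value between 20 and 14 mm. The most extreme rise, from 10 mm, gives about 18%.

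Two stronger readings should be resisted. One is that the fallbacks by themselves give a wrong standard error: with equal variances they do not. The other is that the trial's error rate is 7-13%: that range belongs to one assumed family of SD paths in a branch that may never be reached.

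The planned primary model is sound, and the fallback is pre-specified and ordered. This is a cheap improvement of low severity. It is worth making before unblinding, because a covariance structure chosen afterwards would carry little weight.

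**What to change.** In SAP 2.5.2, state the fallback order as heterogeneous Toeplitz (TOEPH), then heterogeneous AR(1) (ARH(1)), then heterogeneous compound symmetry (CSH), with Kenward-Roger retained. Only if none of these converges, use a homogeneous structure with an empirical (sandwich) standard error, and name a degrees-of-freedom method compatible with it, since Kenward-Roger is a model-based adjustment. The supplementary and subgroup analyses inherit the change through their existing cross-references.

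The cost is a short SAP edit and 11 extra variance parameters, in the fallback only. Heterogeneous compound symmetry may be somewhat conservative if correlation decays with time. Nothing changes if the unstructured model converges.
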